1. OBJECTIVES

Disclosing Recovery: A Decision Aid and Toolkit is a patient decision aid that was developed to help people in treatment for OUD make key decisions regarding disclosure and build skills to disclose.

- Primary aims of the current pilot randomized controlled trial are to examine the implementation of the intervention to inform a future efficacy trial. More specifically, participants' perceptions of the intervention's acceptability and feasibility will be assessed. Additionally, the intervention's impact on decision-making quality will be assessed.
- Secondary aims are to explore the intervention's impact on relationship characteristics, including social support and enacted stigma, and commitment to sobriety.

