2. DESIGN

This is a pilot, parallel randomized controlled trial. Data will be collected from participants at two time points, spaced one month apart, by a research assistant. All participants will be recruited from the waiting room at Brandywine Counseling & Community Services. The research assistant will **screen** interested individuals for eligibility in person (recruitment strategy described below) and schedule study appointments, which may be coordinated with treatment appointments. All study screening and appointments will be conducted in private spaces (i.e., otherwise empty conference room and/or offices) at Brandywine Counseling & Community Services. Participants will receive \$50 gift certificates for completing each time point, and a \$10 bonus gift card for completing both time points within 1 week of when it was scheduled.

At the **first study appointment**, the research assistant will introduce the study, check for questions, and obtain consent for the study procedures, and follow up procedures. Participants will be assured that study data will be kept confidential (including from clinic staff). Participants will be randomly assigned to receive either the disclosure intervention (n=25) or a control intervention (i.e., an evidence-based mindfulness intervention, n=25).

- Disclosure Condition: Participants will be guided through a workbook and accompanying worksheet designed to help them: (1) decide whether or not they want to share information about their substance use with others, and (2) build skills for disclosing (e.g., planning what to say). Importantly, the intervention is not designed to encourage participants to disclose or not disclose (please see intervention booklet included with this protocol submission), but rather to help participants decide whether they want to disclose based on their own goals and values. Our intervention is an adaptation of a previously published disclosure intervention (i.e., the CORAL), which is associated with reduced decisional conflict surrounding disclosure and greater job retention (Henderson et al., 2013).

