3. METHODS

We aim to recruit 50 adults receiving SUD treatment. People in recovery will be eligible if they are:

- 18 years or older;
- currently receiving outpatient treatment at Brandywine Counseling & Community Services;
- are considering disclosing their SUD recovery status to at least one person in the next month;
- have access to a phone that can receive text messages and phone calls;
- and have no current diagnosis of severe mental illness.

Participants will be recruited from Brandywine Counseling and Community Services. Brandywine Counseling and Community Services serves approximately 3,000 clients per year. The study will be advertised via recruitment flyers that will be available in waiting rooms and distributed to clients. Participants will be instructed to contact a research assistant, who will be available in waiting rooms, if they are interested in participating in the study. Participants will also have the opportunity to email or call the study team to express interest in the study. Individuals who indicate interest in the study will be asked to fill out an electronic screener in a private room. After answering several questions on an iPad, individuals will be notified whether or not they are eligible to participate. The research assistant will not have access to individuals' individual answers – they will only be able to access information regarding whether individuals are eligible or not.

When eligible individuals sign up for the study, we will ask for permission to send them a reminder text the day before their scheduled appointment. A reminder text will only be sent to participants who agree to be contacted.

People with self-reported bipolar I disorder and schizophrenia will not be eligible to participate in the sample of people in recovery given that relational processes for these individuals may not generalize to others in recovery from SUDs. People with mood and anxiety disorders will be eligible.

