4. STATISTICAL ANALYSIS PLAN

Participant characteristics will be explored using descriptive statistics. Primary and secondary outcomes will be evaluated with t-test and chi-square tests comparing participants in the *Disclosing Recovery* versus comparator conditions. Because opioid use is hypothesized to impact interpersonal interactions, we will additionally explore whether baseline opioid use moderates associations between intervention assignment with relationship outcomes with two-

way analyses of variance (ANOVA). Statistically significant associations will be further explored. Primary analyses will include the full sample of participants, and secondary analyses will include the full sample of participants for preliminary efficacy analyses or participants who completed the second appointment only for relationship outcome analyses.

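### Optional improvement: adjust the t-test comparison of continuous relationship outcomes for baseline opioid use, which the plan now uses only as an exploratory moderator

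*Combined protocol and SAP*

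**What the plan says.** Section 4 (Statistical Analysis Plan) states that "Primary and secondary outcomes will be evaluated with t-test and chi-square tests" between the two conditions, and names no covariate. The secondary aims in Section 1 are exploratory and cover "relationship characteristics, including social support and enacted stigma". For these outcomes, Section 4 uses "participants who completed the second appointment only for relationship outcome analyses".

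Baseline opioid use appears in one place. Section 4 gives the reason, "Because opioid use is hypothesized to impact interpersonal interactions", and then the analysis: "we will additionally explore whether baseline opioid use moderates associations between intervention assignment with relationship outcomes", by two-way ANOVA. The plan does not name an arm effect from that ANOVA as an estimate to report.

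On allocation, Section 2 says "Participants will be randomly assigned to receive either the disclosure intervention (n=25) or a control intervention", and the control arm is also 25. It mentions no balancing on opioid use. The plan gives no power, effect size, SD, expected retention or prevalence of opioid use.

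That the t-test is the main comparison and is unadjusted is inferred: no covariate is named, and the ANOVA is introduced as an additional exploration.

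**The concern.** The plan names a variable that may predict the relationship outcomes and needs it for its own ANOVA, but leaves it out of the main between-arm comparison. With at most 25 per arm, and fewer after drop-out, a prognostic baseline variable can buy a little precision at almost no cost.

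The restriction to second-visit completers adds a second reason. If opioid users drop out at different rates in the two arms, completers differ by arm in opioid use, and the unadjusted difference shifts. A model containing opioid use removes that part of the shift.

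What is at stake is the quality of exploratory estimates that may inform a later trial. The point covers continuous relationship outcomes only, not binary outcomes or the full-sample analyses.

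**Working it through.** **Inputs.** From the documents: 50 participants in total (Section 3), 25 per arm (Section 2), completers only for relationship outcomes (Section 4). There is no stated figure to reproduce. Assumed: two-sided 0.05, total SD 1, arm difference 0.5 SD, opioid use as two levels with prevalence p of 20% or 40%, and a user versus non-user gap g of 0 to 0.8 SD.

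**1. Precision formula.** The correlation of opioid use with the outcome is r = g × √(p(1−p)). Adjusting multiplies the variance of the arm difference by about (1 − r²)(1 + 1/(N−4)).
- N=50, p=0.4, g=0.8: r² = 0.24 × 0.64 = 0.154. Width ratio = √(0.846 × 1.0217) = 0.93, so about 7% narrower.
- N=50, p=0.2, g=0.8: r² = 0.16 × 0.64 = 0.102. Width ratio = √(0.898 × 1.0217) = 0.96, so about 4% narrower.
- N=50, g=0: √1.0217 = 1.011, so about 1% wider.

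**2. Break-even.** Setting the variance factor to 1 gives r² = 1/(N−3): r = 0.146 at N=50 and 0.164 at N=40. Then g = r/√(p(1−p)):
- p=0.4: 0.146/0.490 = 0.30 and 0.164/0.490 = 0.34 SD.
- p=0.2: 0.146/0.400 = 0.36 and 0.164/0.400 = 0.41 SD.

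**3. Simulation, 20,000 trials per setting.** 95% CI half-width in SD, with power in brackets:

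| Setting | Gap | t-test | Arm + opioid use |
|---|---|---|---|
| N=50, 40% use | 0 | 0.566 (41.3%) | 0.573 (40.7%) |
| | 0.3 | 0.566 (41.0%) | 0.566 (40.7%) |
| | 0.5 | 0.566 (41.1%) | 0.555 (42.8%) |
| | 0.8 | 0.566 (40.3%) | 0.527 (45.7%) |
| N=50, 20% use | 0 | 0.567 (40.7%) | 0.573 (39.9%) |
| | 0.8 | 0.565 (40.9%) | 0.542 (44.0%) |
| About 40 completers, 40% use | 0 | 0.639 (33.1%) | 0.648 (32.5%) |
| | 0.3 | 0.638 (33.6%) | 0.641 (33.4%) |
| | 0.5 | 0.638 (34.5%) | 0.629 (35.2%) |
| | 0.8 | 0.635 (33.5%) | 0.596 (37.2%) |

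The completer rows assume 65% of users and 90% of non-users are retained: 50 × (0.4 × 0.65 + 0.6 × 0.90) = 40.

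**4. Arm effect from the ANOVA with interaction.** If it is averaged equally over users and non-users, its variance is σ²/4 × Σ(1/cell size).
- Cells of 5 and 20 per arm: ¼ × 2 × (1/5 + 1/20) = 0.125, against 2/25 = 0.080 for the t-test. The standard error is √(0.125/0.080) = 1.25 times as large before any gain from r².
- Cells of 10 and 15 per arm: 0.083, a ratio of 1.02.

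With chance variation in cell sizes, simulated half-widths at N=50 are 0.72 to 0.76 SD at 20% use and 0.55 to 0.59 SD at 40% use. An arm effect adjusted for opioid use without the interaction (Type II) avoids this. Apart from the residual term, it is the additive estimate.

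**5. Completer shift.** Assume 40% use, non-users retained 90% in both arms, and users retained 80% in one arm and 50% in the other. Users among completers:
- 0.32/(0.32 + 0.54) = 0.372
- 0.20/(0.20 + 0.54) = 0.270

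The shift is g × 0.102: 0.02, 0.03, 0.05 and 0.08 SD at gaps of 0.2, 0.3, 0.5 and 0.8 SD. In simulation the adjusted estimate was unbiased to within 0.001. With equal retention by arm the shift is zero.

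**The case against.** The case for leaving the plan alone is strong. These are exploratory secondary outcomes of a 50-person pilot. At about 40 completers, a 0.5 SD gap moves the half-width only from 0.638 to 0.629 SD and power by under one point. The documents give no gap, so they cannot show whether adjustment helps or slightly hurts. The retention contrast behind the shift is assumed, and the design supports retention: a one-month interval, payment for each time point with a bonus, and a second visit possible by phone. All of this stands, and it is why the point is optional.

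A reader might infer more, and the documents do not support it:
- **That the t-test is wrong or biased.** Assignment is random, so the unadjusted comparison is valid. A shift needs drop-out that differs by arm in a way related to the outcome, and nothing in the plan indicates that.
- **That the plan expects a strong prognostic effect.** Section 4 hypothesizes an impact on interpersonal interactions as its reason for testing moderation. It does not say that baseline opioid use strongly predicts support or stigma scores, so a gap above break-even cannot be read from it.
- **That the planned ANOVA gives a poor arm estimate.** That holds for an equal-weighted effect, which Section 4 does not specify.
- **That adjustment would repair the power.** Gains beyond about 7% need a gap above 0.8 SD. Explaining 20% of the variance at 40% use takes √(0.20/0.24) = 0.91 SD.

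**Conclusion.** The point holds as a cheap, optional improvement to the continuous relationship-outcome analyses. Over assumed gaps of 0 to 0.8 SD and 20% to 40% opioid use, the effect on interval width runs from about 1% wider to about 7% narrower, with break-even near 0.3 to 0.4 SD. Protection against a completer shift is worth 0.02 to 0.08 SD in the assumed scenario, against a half-width of about 0.64 SD, and nothing if retention is equal by arm. Drop-out from other causes related to the outcome is untouched. All of these sizes rest on assumed inputs. No stated power or decision depends on these outcomes, so the point ranks below any error in the plan. Adjustment for the baseline value of each outcome cannot be judged, because the plan does not say whether these outcomes are also measured at baseline.

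**What to change.** For continuous relationship outcomes, state before outcome data are examined that the main estimate is the arm difference, with 95% CI, from a linear model with arm and baseline opioid use and no interaction. Code opioid use as in the ANOVA. Keep the two-way ANOVA interaction as exploratory. If an arm effect is reported from the ANOVA, do not use the equal-weighted one; use the effect adjusted for opioid use without the interaction. Add that the completer estimate assumes drop-out depends on nothing else related to the outcome.

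Binary outcomes can stay with the chi-square test. In an assumed check with 25 per arm and 40% use, the SD of the risk difference was 0.136 to 0.137 unadjusted and 0.134 to 0.138 adjusted, so there is no material gain. A table of second-visit retention by arm and baseline opioid use would help readers, but that is a separate reporting request.

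The cost is two or three sentences, little programming, no new data and one degree of freedom. If opioid use is not prognostic, the half-width rises from 0.566 to 0.573 SD at N=50, or from 0.639 to 0.648 SD at about 40 completers, and power falls by under one point.
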